	TABLE 2: SEVERITY GRADING.....	43
14.	REFERENCES.....	48

SYNOPSIS

TITLE	Phase II. Dose Ranging Study of the Safety and Efficacy of Orally Administered Lyophilized Fecal Microbiota Product (PRIM-DJ2727) for the Treatment of Recurrent Clostridium difficile Infection (CDI)
PROTOCOL	HSC-SPH-17-0614
SETTINGS	Attending physicians will refer their patients with recurrent CDI (RCDI) for treatment with study drug (PRIM-DJ2727) and will continue to make clinical decisions related to overall health of their patients. Patients with RCDI can self-refer but must have attending physician who will provide non-transplant care. All subjects undergoing therapy will be handled as outpatients at the Kelsey-Seybold Clinic – Main Campus on [name] or University of Texas School of Public Health, Center for Infectious Diseases.
STUDY PURPOSE	The purpose of the study is to determine the safety and efficacy of three different doses of lyophilized intestinal bacteria given orally in capsules for therapy in subjects with recurrent C. difficile Infection (RCDI).
STUDY DESIGN	Allocation: Randomized Endpoints: Safety, preliminary efficacy in preventing future bouts of CDI and improvement in intestinal flora diversity Intervention Model: Parallel assignment Masking: Double-blinded Primary Purpose: safe cure of CDI
STUDY SCHEDULE	Three hundred (360) eligible subjects (1:1:1:1 ratio) with recurrent CDI will be randomly assigned to receive PRIM-DJ2727 lyophilized intestinal bacteria capsules orally in one of 3 dosage schedules: microbiota from 50g stool microbiota/day for 2 consecutive days; 100g stool microbiota for the 1 st day and 50g for the 2 nd day; 100g stool/day for 2 consecutive days with bowel preparation and Imodium; and a 4 th control group will receive 100g stool/day for 2 consecutive days without bowel preparation and Imodium. An aliquot (2mL) of stool sample collected before dosing and at follow-up days 1,7,14,30,60 and 90 after FMT will be stored at -80°C for future analysis (e.g. microbiome studies)
INCLUSION CRITERIA	All subjects 1. Male and female subjects 18 years of age or older. 2. Sexually active male and female subjects of childbearing potential agree to use an effective method of birth control during the study. 3. Female subjects of childbearing potential must have a negative pregnancy test on the day of the procedure prior to administration of study drug. 4. Subject/LAR willing and able to provide informed consent. 5. Able to follow study procedures and follow-ups. 6. Subject must have an attending physician who will provide non-transplant care. 7. Medical history of ≥ 3 bouts of CDI in outpatient or ≥ 2 bouts of CDI in inpatient with either group having ≥ 2 positive fecal tests for C. difficile toxin and at least one bout of CDI within 6 months of enrollment. 8. Received at least two courses of standard-of-care antibiotic therapy for CDI. 9. Have a refrigerator at home to store the second dose of FMT overnight.

EXCLUSION CRITERIA	
 1. Unable to take capsules orally. 2. Requiring systemic non-C. difficile antibiotic therapy within 14 days prior to FMT. 3. Unwilling to stop taking non-dietary probiotics 24-96 hours prior to FMT. 4. Unable to stop taking bile acid sequestrants (e.g. cholestyramine) 24-96 hours prior to FMT. 5. Unable to stop use of drugs with CDI activity: oral vancomycin, oral or IV metronidazole, fidaxomicin, rifaximin or nitazoxanide 24-96 hours prior to FMT and after FMT. 6. Receipt of CDI monoclonal antibodies as treatment for the most recent bout of CDI. 7. Life expectancy of < 6 months. 8. In the opinion of investigator, subject for any reason, should be excluded from the study.
DURATION OF FOLLOWUP	The duration of study participation for each subject is up to 216 days including screening (14 days), treatment (2 days) and follow-up (180-200 days).
STUDY POPULATION	The target population are adults (≥ 18 years old) with ≥ 3 bouts of CDI in outpatients or ≥ 2 bouts of CDI in an inpatient with either group having ≥ 2 positive fecal tests for C. difficile toxin and at least one bout of CDI within 6 months of enrollment.
STUDY BLINDING	This is a double-blinded study for the groups randomized to receive pre-treatment bowel prep and Imodium.
DEFINITION OF TREATMENT FAILURE	Treatment failure is defined as the presence of diarrhea (passage of ≥ 3 watery stools per 24-hour period for two consecutive days) and C. difficile toxin A/B positive stool within 60 days of FMT treatment plus receipt of anti- C. difficile antibiotics.
STUDY AGENT, DOSE OF ADMINISTRATION	
Processed intestinal bacteria from a screened healthy donor will be administered lyophilized FMT to be given by the oral route. FMT will be given as follows:
 
 1. Group 1: With bowel prep and Imodium 1st treatment day, lyophilized product generated from 50g of stool 2nd treatment day, lyophilized product generated from 50g of stool 2. Group 2: With bowel prep and Imodium 1st treatment day, lyophilized product generated from 100g of stool 2nd treatment day, lyophilized product generated from 50g of stool 3. Group 3: With bowel prep and Imodium 1st treatment day, lyophilized product generated from 100g of stool 2nd treatment day, lyophilized product generated from 100g of stool 4. Unblinded Group 4: (Without bowel prep and Imodium) 1st treatment day, lyophilized product generated from 100g of stool 2nd treatment day, lyophilized product generated from 100g of stool
EFFICACY EVALUATION	
Primary Endpoint:
 
 • Safety of FMT (lyophilized capsules with various doses) • Prevention of subsequent bouts of CDI in 60 days post FMT. • Safety of FMT (lyophilized capsules with same doses) without using pre-FMT bowel preparation and Imodium • Prevention of subsequent bouts of CDI in 60 days post FMT without using pre-FMT bowel preparation and Imodium. 
Secondary Endpoint:
 
 • To characterize improvement in microbiota diversity from baseline in subjects treated with various doses of lyophilized capsules.

SAFETY EVALUATION	To ensure safe study conduct during the study, an independent, non-blinded, external Data and Safety Monitoring Board (DSMB) will be established to perform safety evaluations on an ongoing basis. A DSMB charter will be developed and will detail the review of the safety data. The DSMB will have the power to stop the trial.
STUDY STOPPING RULES	Study may be halted or discontinued if the DSMB identifies a trend of more illnesses or side effects in one or more of the treatment groups.

1. INTRODUCTION

1.1 Background

During the past several years, *C. difficile* Infection (CDI) has become more frequent and severe, more refractory to standard therapy, with predictable recurrence rates of 25% after standard therapy^{1,2}. It is now accepted that the disruption of the normal balance of colonic microbiota secondary to antibiotics facilitates the development of CDI and improvements in the diversity and quantity of microbiota is associated with recovery of infection and prevention of disease recurrence. Studies have shown that subjects with recurrent CDI (RCDI) have decreased diversity of colonic flora with absolute reductions in counts of anaerobic species of *Bacteroidetes* and *Firmicutes* in their stool compared to subjects recovering from single episodes of CDI³. Numerous case reports and retrospective case series have demonstrated the benefit of intestinal microbiota transplantation (FMT) in subjects with severe or RCDI with cure rates over 80%-90%⁴⁻⁸, making FMT standard therapy when multiple recurrences are seen⁹. FMT involves administration of a suspension of intestinal bacteria obtained from a healthy individual into the GI tract of a patient with RCDI to promote normalization of flora⁶.

1.2 Our Previous Study (HSC-SPH-13-0119 and HSC-SPH-14-0020)

Fecal Microbiota Transplantation Delivered by Colonoscopy

A recently published study by our group found a single infusion of 50 g fresh, frozen or lyophilized fecal microbiota product obtained from a small number of healthy donors in the treatment of 72 patients with recurrent CDI given by colonoscopy led to cure in 87%¹⁰.

Our data from the recently published study suggested certain *Firmicutes* taxa might be negatively associated with CDI, which was consistent with the results of a previous study¹¹. Noticeable changes in microbiota structures occurred by 7 days after FMT when the structures of the SUBJECTs closely resembled those of the donors. We observed multiple microbes at the family level consistently enriched in subjects with recurrent CDI after receipt of FMT: *Lachnospiraceae*, *Ruminococcaceae* and *Bacteroidaceae*. These bacteria are known to be dominant and are established early in life as key members of the human faecal microbiota. They are thought to play major ecologic roles in establishment and maintenance of colonic epithelial health^{12,13}. *Lachnospiraceae* has also been

observed in an experimental animal model to suppress *C. difficile* ¹⁴. It will be important to determine the microbial composition at a finer species or strain level to better understand more fundamentally what is happening with FMT.

The unique findings of our study were the comparative clinical efficacy and improvement of intestinal microbiome profiles resulting from the use of fresh, frozen and lyophilized donor microbiota products in the treatment of RCDI using a small number of non-related donors providing each product. Rates of cure were slightly less with the lyophilized product but well within the range of cures seen in the literature with fresh product ¹⁵. We demonstrated equivalent efficacy in a small number of donors supporting other studies showing non-related donors with a healthy microbiome are suitable sources of microbiota for FMT in patients with dysbiosis.

Lyophilized microbiota are of particular interest for FMT because of their potential for prolonging storage time, and more importantly, oral administration in non-frozen capsules with lower volume resulting in the need to ingest fewer capsules ¹⁶. We hypothesize the slightly reduced efficacy of lyophilized material in this study related to loss of microbiota during the freezing process. We are currently exploring the use of lyophilized product given in capsules using a higher content of faecal microbiota and using a non-polyol cryoprotectant, which has been reported as possibly stabilizing culturable microbiota during the freezing process ¹⁷. The frozen product was effective in the present study without the use of cryoprotectants, and we do not know the effect of low temperatures on the anaerobes of most importance in FMT. Damage from long-term freezing of faecal bacteria has been shown to be lessened by adding 10% glycerol to the samples ¹⁸. We found that glycerol cannot be used in product to be lyophilized.

Lyophilized microbiota are of particular interest for FMT because of their potential for prolonging storage time, and more importantly, oral administration in non-frozen capsules with lower volume resulting in the need to ingest fewer capsules ¹⁶. Lyophilized capsules were effective in the present study without the use of cryoprotectants, and we do not know the effect of low temperatures on the anaerobes of most importance in FMT. However, we are currently exploring the use of lyophilized product given in capsules using a higher content of fecal microbiota, using a cryoprotectant, to stabilize the microbiota during the freezing process ¹⁷. Lyophilized donor fecal microbiota have been used successfully in a small number of people suffering from recurrent CDI in a case report and one small series ^{19,20} and need further study.

FMT by Oral Capsules of Lyophilized FMT Product versus Enema using Frozen FMT Product

In an ongoing study, 8 patients with RCDI were administered orally of 5g of lyophilized FMT product derived from 100g of fresh stool and 21 RCDI patients were given frozen product (via enema) obtained from 100g of fresh stool. Cure was seen in 5 of 8 (63%) for the oral product and 20 of 21 (95%) for the frozen product given by enema. We then increased the dose of lyophilized product to 10g given over 2 consecutive days (5g each day, derived from a total of 200g of fresh stool per treatment). We saw cure in 10 of 11 (91%) of treated subjects. This study demonstrated effectiveness of a single infusion via enema of frozen or lyophilized fecal microbiota capsules obtained from a small number of healthy donors in the treatment of recurrent CDI. Frozen FMT product has become widely used for microbial restoration in recurrent cases of CDI ²¹ and was shown to be equivalent to fresh donor product in a randomized double-blind comparison in 219 patients with recurrent CDI ²².

In vivo Study to Determine Storage Time for Frozen and Lyophilized FMT Product

Mice were divided into four groups for each storage time point assay, with each group containing 5 mice. The study design and time line are illustrated in Figure 1. All mice were treated with a mixture of antibiotics dissolved in drinking water. The mixture contained kanamycin (2 mg/day), gentamycin (0.175 mg/day), metronidazole (35 mg/kg/day) and vancomycin (40 mg/kg/day) (Thermo Fisher Scientific, Waltham, MA). The antibiotic treatment started at day -4 and continued for three days. Mice were then fed regular water with clindamycin (10 mg/kg) (Chem-Impex International Inc., Wood Dale, IL) until day zero when *C. difficile* by gavage was administered via intraperitoneal injection of 1.5×10^5 colony-forming units (CFU) followed by FMT products. The time interval between *C. difficile* challenge and FMT administration was 30 to 60 minutes. The total volume for each gavage was less than 0.2 ml. The positive control of CDI disease group was fed with *C. difficile* alone in saline. The positive therapeutic control group was treated with fresh product. The test groups were treated with either frozen or lyophilized products stored for different time intervals (7, 9, 11 or 15 months). The mice were followed-up for clinical diarrhea occurrence (excretion of soft wet, unformed with moderate perianal staining of the coat, or watery without solid pieces stool) ²³. Fecal samples were collected at various time points and immediately stored at -80°C for further analysis. The FMT products' efficacies were measured by time required to develop diarrhea after *C. difficile* challenge

We attempted to determine changes in major microbiota groups after freezing or lyophilization and storage for various lengths (7, 9, 11 or 15 months) by neutralization of CDI in mice experimentally infected. After antibiotic disruption of the intestinal microbiota, 27/27 (100%) of the mice treated only with *C. difficile* developed diarrhea within 2 days of challenge. Diarrhea occurred in the following number of challenged mice given fresh, frozen or lyophilized FMT product stored for 7 months, respectively: 0/22 (0%); 0/5 (0%); and 0/5 (0%) ($p=1.00$). The number of mice developing diarrhea with 95% confidence interval and statistical results comparing frozen with the fresh FMT product stored 9 months 3/5 (60%, 3, 95% CI: 1-6, $p=0.0911$), 11 months 5/5 (100%, 2, 95% CI: 2-3, $p=0.0040$), and 15 months 3/5 (60%, 2, 95% CI: 2-6, $p=0.0566$, frozen, 15 months). The values for lyophilized products stored at 9 months were 2/5 (40%, 6, 95% CI: 1-6, $p=0.1756$), lyophilized, for 11 months 3/5 (60%, 2, 95% CI: 1-6, $p=0.1095$) and for 15 months 2/5 (40%, 3, 95% CI: 2-3, $p=0.0110$). When comparing frozen and lyophilized products stored up to 7 months, there was no significant difference, with OR equal one (1.00) for both products. Both products showed a reduction in CDI neutralization after 7-month storage time.

2. OBJECTIVE

Primary endpoints of the study are to evaluate the safety of lyophilized product by capsules with various doses and the prevention of subsequent bouts of CDI in 60 days post FMT; and to evaluate the safety of lyophilized product by capsules with same doses without bowel preparation and Imodium, and the prevention of subsequent bouts of CDI in 60 days post FMT without bowel preparation and Imodium. The secondary endpoint is to characterize improvement in microbiota diversity from baseline in subjects treated with various doses of lyophilized capsules.

Lyophilized FMT intestinal bacteria inoculate from well-screened healthy volunteer donors providing ≥ 100 grams of stool/FMT will be generated. Donor intestinal bacteria suspensions will be diluted (1:5 dilution) ≥ 500 mL for later lyophilization and encapsulation. Fecal samples from donors and recipients will be saved for future studies (e.g. microbiome analysis).

3. STUDY DESIGN

This is a single center, randomized, parallel assignment, double-blinded, safety and

efficacy study to be conducted in subjects with recurrent CDI. Approximately 360 subjects will be enrolled in the study and randomized at 1:1:1:1 ratio to receive lyophilized donor intestinal bacteria with various doses (group 1 receiving healthy microbiota collected from 50g stool for 2 consecutive days; group 2 receiving healthy microbiota collected from 100g stool on the 1st day of treatment and from 50g stool on the 2nd day of the treatment; group 3 will receive healthy microbiota collected from 100g stool for 2 consecutive days using bowel prep and Imodium. An unblinded group 4 will receive healthy microbiota collected from 100g stool for 2 consecutive days without using bowel preparation and Imodium. All subjects will be followed for approximately 180-200 days following FMT treatment for safety.

3.1 Study Structure

Recipient subjects must have a physician who agrees to accept care of the patient following FMT. Subjects consenting to treatment at Kelsey-Seybold Clinic (KSC) and the University of Texas School of Public Health must be willing to self-pay for the FMT with a money order or cashier's check, or debit/credit card in the amount of \$1,500 (see Section 11). Insurance payment will not be accepted. All subjects will be treated at Kelsey-Seybold Clinic – Main Campus on [name] Once the procedure is completed, the recipient's care will be returned to their attending physician. Letters will be sent to physicians regarding the study and FMT completion.

3.2 Definition of recurrent CDI for Study Entry

The definition of recurrent CDI for study entry is a medical history of ≥ 3 bouts of CDI in outpatients or ≥ 2 bouts of CDI in an inpatient with either group having ≥ 2 positive fecal tests for *C. difficile* toxin and at least one bout of CDI within 6 months of enrollment. Two of the three bouts must have a positive fecal *C. difficile* toxin test and one of the three bouts should be within 6 month of enrollment.

3.3 Outcome Measure

Fecal microbiota diversity and phyla and family will be measured at the Alkek Microbiome Center at Baylor College of Medicine or other qualified laboratory (to be clarified on form 1572). A number of clinical and safety endpoints will be examined during the trial related to worsening of underlying disease and events common in this population. Additionally we will look for symptoms of worsening diarrhea and test *C. difficile* toxins A/B.

3.4 Data Safety and Monitoring Board

A committee of 3 faculty level people will serve as the DSMB reviewing primary and

secondary parameters and data from the study. Safety will be the greatest concern. The DSMB has the capacity to stop the study. The Board will meet at least three times during the study: At the study beginning; after 8-10 patients in each group have been studied and at the completion of the study (all subjects reached 180-200 days follow-up after FMT).

Professional	Name
Pharmacist	[name]
Epidemiologist	[name]
Clinical Infectious Diseases Specialist	[name]

4. SUBJECTS

SELECTION AND WITHDRAWAL

4.1 Inclusion Criteria

- 4.1.1 Male and female subjects 18 years of age or older.
- 4.1.2 Sexually active male and female subjects of childbearing potential agree to use an effective method of birth control during the study.
- 4.1.3 Female subjects of childbearing potential must have a negative pregnancy test on the day of the procedure prior to administration of study drug.
- 4.1.4 Subject/LAR willing and able to provide informed consent.
- 4.1.5 Able to follow study procedures and follow-ups.
- 4.1.6 Subject must have an attending physician who will provide non-transplant care.
- 4.1.7 Medical history of ≥ 3 bouts of CDI in outpatient or ≥ 2 bouts of CDI in inpatient with either group having ≥ 2 positive fecal tests for *C. difficile* toxin and at least one bout of CDI within 6 months of enrollment.
- 4.1.8 Received at least two courses of standard-of-care antibiotic therapy for CDI.
- 4.1.9 Have a refrigerator at home to store the second dose of FMT overnight.

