- Enrollment visit will occur on day -14 to -1 during which the informed consent will be obtained; inclusion and exclusion criteria will be reviewed; demographics, current medications, the medical history, and the CDI history (including information on solicited symptoms for two-week period prior to enrollment) will be reviewed and recorded. Subjects may already be taking or just have been prescribed antibiotics per standard of care to control recurrent CDI symptoms at the time of enrollment. Subjects who have completed antibiotic therapy will receive four days of oral vancomycin or fidaxomicin daily (PI can call in prescription if needed) prior to the 24-96 hours washout period. A stool collection kit along with IRB approved pretreatment prep instructions, pre-treatment diary, stool collection instructions and directions to drop specimen will be provided to subject.
- A stool sample will be collected by subject during enrollment period (prior to bowel prep) and a pre-treatment diary card will be completed by subject. Study personnel can obtain the stool and diary from subject on treatment Day 1 clinic visit. This stool will go to EPDL at the University of Texas School of Public Health.
- Day -4 to -1 before treatment: remind the subject by email or phone call about clinic appointment time, stopping antibiotic/probiotic/ bile-acid sequestrant, pre-treatment preparation and bringing pre-treatment diary and stool. Day -4 to -1(96 to 24 hours) before treatment: the last day of *C. difficile* antibiotics, non-dietary probiotics and bile-acid sequestrants. Subjects continue taking routine prescription medications.
- Day -1 before treatment: subjects follow a clear liquid diet the entire day. In the evening around 6:00pm, subjects (treatment groups 1-3) who were instructed by the study team during the enrollment will ingest bowel prep.

Treatment Visit: Day 1 (Clinic Visit)

- Subjects are recommended to continue clear liquid diet until after treatment for 1 hour.
- Ensure subject in treatment groups 1-3 has taken bowel prep the evening before and 4mg (2 capsules) of loperamide (Imodium) the morning of treatment (If Imodium

is missed, can be taken within 12 hours of FMT treatment). If bowel prep is missed, subject can proceed with FMT and will be recorded as protocol deviation.

- Collect and review the pretreatment diary with subject to determine baseline pattern of solicited symptoms to assess for adverse events.

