10.2.2 Power Calculations

Assuming recipients receiving 100g for both treatment days, 100g on the first treatment day and 50g on the second treatment, or 50g for both treatment days, or 100g for both treatment days without bowel prep and Imodium has 88%, 80%, 70% and 80% efficacy in preventing post RCDI respectively, it is determined that 348 recipients (1:1:1:1 ratio) would provide 85% power to detect a statistically significant difference in the distributions of efficacy between the 4 treatment groups at the two-sided $\alpha = 0.05$ level of significance. Assuming 10% of patients would be lost to follow-up, 360 (90 in each group) recipients are planned.

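### Entry may admit subjects whose last CDI bout ended more than 60 days before FMT, and the plan never separates them; stratify by time since last bout (optional improvement)

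*Combined protocol and SAP*

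**What the plan says.** **Entry.** The Synopsis and Sections 3.2 and 4.1 require a set number of past bouts, positive toxin tests, and "at least one bout of CDI within 6 months of enrollment". Nothing in Section 4.1 or 4.2 requires an active episode or limits the time since the last course of therapy.

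**Who arrives.** Section 7.2 describes two kinds of subject. Of the first it says: "Subjects may already be taking or just have been prescribed antibiotics per standard of care to control recurrent CDI symptoms at the time of enrollment". Of the second: "Subjects who have completed antibiotic therapy will receive four days of oral vancomycin or fidaxomicin daily", given before the 24-96 hour washout.

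**Endpoint.** Section 2 names "prevention of subsequent bouts of CDI in 60 days post FMT"; the Synopsis and Section 9.11 agree. Treatment failure (Synopsis, Section 6) is counted only after FMT.

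**Randomization and analysis.** Section 10.2.4 uses permuted blocks and names no stratification factor. Section 10.2.3 compares groups 1-3, and groups 3 and 4, in everyone who started the procedure. Sections 10.2.3 and 10.2.6 name no covariate, stratum or subgroup for efficacy. CDI history, including test results and treatment, is taken at enrollment (Sections 7.2 and 8.1), but the analysis makes no use of it.

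**The concern.** The criteria allow a last bout that ended anywhere from days to nearly six months before enrollment. A subject who has been well for more than 60 days may be at a different recurrence risk from one still being treated. If that risk is low and responds little to dose, such subjects raise the success rate in every group and pull the groups together. The trial has no placebo arm, so the difference between doses is the efficacy result, and a smaller difference makes dose selection harder. The number of such subjects can also differ between groups by chance.

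**Working it through.** **1. The plan's own figure.** Section 10.2.2 assumes that 100+100 g, 100+50 g, 50+50 g and 100+100 g without bowel preparation and Imodium "has 88%, 80%, 70% and 80% efficacy in preventing post RCDI respectively", and states that "348 recipients (1:1:1:1 ratio) would provide 85% power". For a four-group Pearson chi-square test with 87 per group:
- Mean rate = (0.88 + 0.80 + 0.70 + 0.80)/4 = 0.795.
- Sum of squared deviations = 0.085² + 0.005² + 0.095² + 0.005² = 0.0163.
- Noncentrality = 87 × 0.0163/(0.795 × 0.205) = 8.70 on 3 df, so power is 69.5% (71.1% at 90 per group).

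The stated 85% does not reproduce. That is a separate matter, but it means there is no power in reserve.

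**2. Dilution model.**
- From the plan: p = 70/80/88% for groups 1, 2 and 3; 90 per group; two-sided alpha 0.05.
- Assumed, not in the documents: a share f with success rate q = 95% at any dose, and the plan's rates in everyone else.
- Observed rate in a group = (1 − f)p + fq.
- Group 3 minus group 1 = (1 − f)(0.88 − 0.70) = 0.18(1 − f), whatever q is.

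**3. Power.** I use a three-group linear trend test, which the plan does not name, because it suits ordered doses and starts near the plan's 85%. With m the mean of the three rates:

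power = Φ[(d − 1.96·s0)/s1], where d = p3 − p1, s0 = √(2m(1 − m)/n), s1 = √([p1(1 − p1) + p3(1 − p3)]/n).

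- f = 0: d = 0.180, s0 = 0.0604, s1 = 0.0592, power 85%.
- f = 20%: d = 0.144, s0 = 0.0567, s1 = 0.0560, power 72%.

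Simulation gives values within about a point of these. It also gives the power of the test stratified by recency, and of the test in recent-bout subjects alone:

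| f | Rates, groups 1/2/3 (%) | Group 3 − 1 (points) | Unstratified | Stratified | Recent-bout only |
|---|---|---|---|---|---|
| 0 | 70.0/80.0/88.0 | 18.0 | 86% | 86% | 86% |
| 5% | 71.3/80.8/88.4 | 17.1 | 83% | 83% | 84% |
| 10% | 72.5/81.5/88.7 | 16.2 | 80% | 81% | 82% |
| 20% | 75.0/83.0/89.4 | 14.4 | 73% | 74% | 77% |
| 30% | 77.5/84.5/90.1 | 12.6 | 64% | 66% | 71% |

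**4. Sensitivity.** With q between 90% and 100%, unstratified power is 71-75% at f = 20% and 61-68% at f = 30%. Stratifying adds about 0-3 points over that range. For the four-group test with 87 per group and q = 95%, power goes from 69.5% to 62.1%, 54.1% and 45.7% at f = 10%, 20% and 30%.

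**5. Chance imbalance.** At f = 20%, the SD of the difference in share between two groups is √(2 × 0.2 × 0.8/90) = 6 points. Multiplied by a success gap of 7 points (95 − 88) to 25 points (95 − 70), this shifts a comparison by roughly 0.4 to 1.5 points. That is small.

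**The case against.** Several objections have force.

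- **The share is unknown.** A reader might infer that some enrolled subjects had already passed a 60-day recurrence window. The criteria permit this, but nothing in the documents reports it. At f = 5-10% the loss is only about 3-6 points of power.
- **The four-day course matters.** Completed-therapy subjects receive vancomycin or fidaxomicin shortly before FMT, and Section 1.1 names antibiotic disruption of the microbiota as what facilitates CDI. An earlier quiet period therefore does not establish low risk afterwards. If the course restarts risk, dilution is smaller.
- **The endpoint starts at FMT.** A reader might also infer that such a subject had met the success definition without treatment. The documents do not support this, because only the 60 days after FMT count.
- **The planning rates may already be mixed.** Section 10.2.2 states its rates for this trial's recipients, and the entry criteria of the earlier capsule study (Section 1.2) are not given. If 70/80/88% already describes the mixed population, nothing is lost against plan.
- **No arm is favored.** Randomization keeps the groups comparable in expectation.
- **Stratification recovers little power,** and CDI history is already collected, so a subgroup analysis is probably feasible afterwards.

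All of this limits the size of the problem and how firmly it can be stated. It does not remove the point that a permitted source of heterogeneity goes unused, or that a subgroup chosen afterwards carries less weight than one fixed in advance.

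**Conclusion.** The concern holds in limited form. The criteria may admit subjects whose last bout ended more than 60 days before FMT, and no part of the design or analysis identifies them. If their outcome depends little on dose, each 10% of such subjects takes 1.8 points off the 18-point contrast. In the trend-test illustration, power falls from about 86% to 80% at f = 10%, 73% at 20% and 64% at 30%. These figures rest on an assumed share, an assumed 5% failure rate at any dose, planning rates that apply only to the remaining subjects, a test the plan does not name, and a full 90 per group with no loss to follow-up. The harm would be lost contrast and power; the documents do not support a claim of biased arms. This is an optional improvement, not a required change.

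**What to change.** Leave eligibility and pre-treatment as they are.

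- **Sections 7.2 and 8.1:** from the CDI history already collected, record the end date of the last bout or anti-CDI course, not counting any study-related pre-treatment course.
- **Section 10.2.4:** stratify randomization by 60 days or less versus more than 60 days since that date. Measure it at enrollment, where Table 1 places randomization.
- **Section 10.2.6:** stratify the primary efficacy tests by the same factor, report the share in each group, and pre-specify a secondary efficacy analysis in the recent-bout stratum.
- **State the limits:** stratifying recovers only about 0-3 points of power and does not restore the diluted contrast. The recent-bout analysis estimates the undiluted contrast in fewer subjects, with about 77% power at f = 20% and 71% at f = 30% under the same assumptions.

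The cost is one date field, one two-level stratum and a few sentences of analysis text. No extra subjects are needed.
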